4.7.3. Missing Data

As described in Section 8.3, in responder analyses, subjects with missing data will be classified as non-responders. Otherwise, there will be no imputation of missing data.

5. SUBJECT DISPOSITION

5.1. Study Populations

The number and percentage of subjects in each analysis population will be summarized by treatment group. Subject inclusion in each analysis population will be presented in a subject listing.

Reasons for exclusion from the Per Protocol population will be listed.

5.2. Disposition

The number of subjects enrolled in the study by investigator and treatment group will be tabulated. Subject disposition will be summarized by treatment group and will include the number of subjects who were randomized into the study, the number of subjects who completed the study, and the number of subjects who discontinued prematurely (ET) for any of the following reasons:

- Deviation/noncompliance with the protocol or study drug
- Adverse event(s)
- Investigator decision
- Sponsor decision
- Subject withdrawal of consent
- Subject lost to follow up
- Death
- Other

5.3. Protocol Violations

Significant protocol violations will be tabulated displaying frequencies and percentages of the Efficacy population falling into the following categories:

- Treated despite violating inclusion criterion 8 (i.e., screening AAPS of \geq 4)
- Treated with dose other than the dose the subject was randomized to receive
- Developed withdrawal criterion but was not discontinued from treatment
- Less than 80% compliance

6. **DEMOGRAPHICS AND BASELINE CHARACTERISTICS**

6.1. **Demographics**

Demographic and baseline characteristics data (age, height, weight, BMI), social history (smoking, caffeine, alcohol use), medical history (abnormalities only), physical examination (abnormalities only), and concomitant medications at study entry will be listed for all subjects. Demographic and Baseline Characteristics of the Safety and Efficacy populations will be summarized by treatment group and for the overall population.

Baseline for the demographic and baseline characteristic variables will be the last prerandomization value. Continuous variables will be summarized using number of observations (n), mean, SD, median, minimum, and maximum. Frequencies and percentages will be reported for all categorical data. No formal statistical testing comparing treatment groups will be performed.

The following variables will be summarized by treatment group and overall:

Continuous demographic and Baseline characteristic variables: age (years), height (cm), weight (kg), body mass index (BMI; kg/m²), and simple endoscopic score Crohn's disease (SES-CD).

Categorical demographic and Baseline characteristic variables: sex (female or male), ethnicity (Hispanic/Latino or Not Hispanic/Not Latino) and race (American Indian or Alaska Native; Asian; Black or African American; Native Hawaiian or Other Pacific Islander; White; Other, specify) nicotine consumption (never, former, current), and alcohol consumption (never, former, current).

Baseline SES-CD, an optional assessment by colonoscopy, will be presented in subject listing.

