4.3 Packaging, Labeling and Storage

25 mg and 100 mg APD371 capsules will be packaged 30 count in 60-cc HDPE bottles with a heat induction seal and child resistant screw cap. Each subject will be provided with 8 bottles of APD371 packaged drug product for the duration of the study, two bottles being dispensed on Day 1, Day 15, Day 29 and Day 43, respectively. If subjects in the 100 mg cohort are titrated down to a 50 mg dose they may receive additional bottles.

The 50 mg APD371 capsules will also be packaged 30 count in 60-cc HDPE bottles with heat induction seal and child resistant screw cap.

Subjects returning for assessment at the end of Wks 2, 4, 6 should take their morning APD371 medication from their newly dispensed bottles for treatment periods Wks 3-4, 5-6 and 7-8, respectively.

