4.6.1 Dose Interruption and Stopping Rules

Adverse Events (AEs) of supine SBP decrease, supine DBP decrease, postural BP decrease, HR increase and HR decrease will be closely monitored. If such an AE occurs in patients taking the study drug, the Investigator must assess whether the AE meets the study drug interruption/stopping rules and proceed as recommended in the below table.

If the study drug is interrupted due to the criteria described in the table, the patient will be evaluated as part of an unscheduled visit to assess their status and the Investigator will determine next course of action. If necessary, subsequent visits to assess the outcome of the event will be scheduled. Once the re-start criteria are met, study drug will be re-started under medical supervision. Additional visits may be scheduled at the investigator's discretion to more closely monitor patient status.

Any patient that develops postural hypotension will not be discharged from the study site with study drug until the event completely resolves and safety and tolerability of the reduced dose in the patient is confirmed.

Amendment 02 (10 August 2017)

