3. INVESTIGATIONAL PLAN

3.1. Overall Study Design and Plan

This is a Phase 2a study in subjects diagnosed with abdominal pain due to quiescent to mildly active CD. The study design is a randomized, multi center, open-label, parallel group comparison consisting of two cohorts dosed with APD371 in up to a total of 16 subjects (8 subjects in each cohort). Randomization will be stratified by sex. A study plan is provided in Figure 1.

SCREENING TREATMENT FU V5 VISIT SV1 SV2 V1 V2 V4 V6 V9 V3 V7 V8 WEEK W-4 W-1 W0 W0 W1 W2 W4 W6 W10 W8 W8 DAY -D-28 to D-1 -D7 to -D1 D1 D2 -D1 APD371 100 mg TID APD371 50 mg TID APD371 25 mg TID -- ---- APD371 25 mg BID

Figure 1. APD371-004 Study Plan

Subjects will enter a Screening period of up to 28 days during which they will record their APS on a diary card. If their AAPS is \geq 4 and they satisfy all other eligibility criteria, they will be randomized in a 1:1 ratio to receive APD371 doses of 25 mg or 100 mg capsules TID for 8 weeks (until Day 56). If subjects on APD371 100 mg TID experience hypotensive symptoms (systolic blood pressure [SBP] <90 or diastolic blood pressure [DBP] <50 mmHg) at any stage during study treatment, they will be titrated down to 50 mg TID.

Following the first day of treatment subjects will return for weekly safety and tolerability assessments for the first two weeks and then once every other week until the end of the treatment period. Safety assessments will include physical examinations, adverse event (AE) reporting, vital signs, 12-lead electrocardiograms (ECGs) and clinical laboratory tests including blood sampling.

Subjects will record their APS during Screening twice daily for at least 7 consecutive days within the Screening period (Day -28 to Day -1); early morning and late evening (approximately 06:00 - 08:00 and 20:00 - 22:00). During Treatment subjects will record their APS three times a

day on each treatment Day (Day 1 to Wk 8), before the morning dose, at 1.5 hours after the morning dose and before the evening dose.

Subjects will also record their stool frequency on a daily basis.

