4.2. Methods of Assigning Study Participants to Treatment Groups

Subjects who meet all the entry criteria and are eligible for the study will report to the investigator to be randomized on Day 1. Eligible subjects will be randomly assigned to receive 1 of 2 study treatments, either APD371 100 mg TID or APD371 25 mg TID in a 1:1 ratio. The investigator will randomize up to 20 subjects for entry from a sealed envelope held by the Sponsor clinical trial manager.

If a subject in the APD371 100 mg TID group experiences hypotensive symptoms (SBP <90 or DBP <50 mmHg) during the course of study drug treatment, the investigator can instruct the pharmacy to dispense an APD371 50 mg dose. In this situation all other study medication should be returned to the pharmacy.

The analyses for all safety outcomes will use the Safety population which consists of all randomized subjects who received at least 1 dose of study drug; in addition, if a subject is found to have taken a study therapy for the entire duration of the study different from that to which they was randomized, then the subject is counted in the treatment group of the drug they actually received.

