4.5. Analysis Populations

The following analysis sets are defined in this study:

- The Randomized population will include all randomized subjects.
- The Efficacy population will include all randomized subjects who received at least 1 dose of study medication and have completed at least 7 days of assessments of APS on treatment up to Wk 4. The analyses of all efficacy variables will use the Efficacy population.
- The Per Protocol population will comprise all members of the Efficacy population without a major protocol violation that could affect the validity of efficacy assessments. The Per Protocol population will be used for the analysis of selected endpoints indicated in Section 8. The Per Protocol population will be identified prior to database lock.
- The Safety population will include all randomized subjects who received at least one dose of study medication. The analyses of all safety variables will use Safety population.

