7.3. Study Treatment Compliance

Compliance will be assessed using subject data recorded in the drug accountability form of the eCRFs. On each day, a subject should take their assigned treatment. The compliance rate for each subject will be computed as $100\% \times (actual number of tablets taken over the study period)/(designated total number of tablets that should have been taken over the study period). Study period is defined as the number of days that the subject has been in the active treatment phase of the trial. Compliance rates will be summarized for each treatment group and overall.$

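### SAP 5.3 lists dosing off the randomized dose as a significant violation without excepting the plan's own dose reductions, so subjects treated as planned become candidates for exclusion from the Per Protocol set

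*SAP*

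**What the plan says.** Three parts of the SAP bear on this.

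- **Reduction.** SAP 3.1 says of 100 mg TID subjects with hypotensive symptoms (systolic below 90 or diastolic below 50 mmHg) that "they will be titrated down to 50 mg TID". SAP 4.2 covers the same event in permissive terms: "the investigator can instruct the pharmacy to dispense an APD371 50 mg dose". The protocol also foresees reductions. Section 4.3 has "If subjects in the 100 mg cohort are titrated down to a 50 mg dose they may receive additional bottles". Section 4.6.1 holds a subject with postural hypotension at the site until "safety and tolerability of the reduced dose in the patient is confirmed", in wording not limited to one arm.
- **Violations.** SAP 5.3 opens with "Significant protocol violations will be tabulated displaying frequencies and percentages of the Efficacy population falling into the following categories". The second category is "Treated with dose other than the dose the subject was randomized to receive". No exception follows.
- **Per Protocol set.** SAP 4.5 keeps Efficacy-population members "without a major protocol violation that could affect the validity of efficacy assessments" and has the set fixed before database lock. SAP 8.2 and 8.3 repeat the AAPS and responder analyses on it, and SAP 13 adds Per Protocol tables for APS.

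**The concern.** A subject whose dose is lowered as SAP 3.1 directs has then been treated with a dose other than the randomized one. The wording of SAP 5.3 covers that subject, although nobody departed from the plan.

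Two things are at stake. First, the violation table would mix planned safety management with allocation or dispensing errors and so overstate poor conduct. Second, the same subjects become candidates for exclusion from the Per Protocol set. Exclusion would then depend on a blood-pressure event after randomization, one the SAP itself links to the higher dose. The repeated dose comparison would no longer be between groups formed by randomization alone.

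**Working it through.** **Setting the text side by side**

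1. SAP 3.1 makes the step to 50 mg TID an instruction and SAP 4.2 makes it an option. In both, the trigger is written for the 100 mg group only.
2. The second category of SAP 5.3 has no limit on cause or duration. By contrast, SAP 4.2 re-groups subjects in the safety analysis only if they took a different therapy for the whole study. A limit to dispensing or allocation errors in 5.3 has to be supplied by the reader.
3. SAP 5.3 calls these violations significant, while SAP 4.5 excludes for major ones. Major is not defined. The only violations table planned on the Efficacy population, Table 14.1.4 in SAP 13, uses the word major in its title. That is the link between list and set, and it is indirect.
4. SAP 4.5 adds a second test, a possible effect on the validity of efficacy assessments. A halved dose could be judged to meet it. The trial is open-label with sponsor and CRO unblinded (SAP 4.4), so that judgment is made with the arm known.
5. Both documents ask subjects who change dose to go on scoring pain daily (protocol 5.5.1, SAP 3.3.2.1), which suggests their data were meant to be used.

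**Illustration of size**

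The documents give no power calculation, reduction rate or expected Per Protocol loss, so there is no stated figure to reproduce. The planned arm size is 8 (SAP 3.1). All other inputs are assumptions.

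*Responder rate, 100 mg arm, assumed 4 of 8 = 50%:*

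| Reduced subjects removed | All non-responders | All responders |
|---|---|---|
| 1 | 4/7 = 57% | 3/7 = 43% |
| 2 | 4/6 = 67% | 2/6 = 33% |

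If 2 are removed and one was a responder, the rate is 3/6 = 50%, unchanged.

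*Chance that at least one of 8 is reduced, 1 − (1 − p)^8, for an assumed rate p:* 5%, 0.34; 10%, 0.57; 20%, 0.83; 30%, 0.94; 40%, 0.98. The expected number, 8p, runs from 0.4 to 3.2.

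*Precision if k reduced subjects leave the 100 mg arm.* The 95% CI half-width for a simple two-sample mean difference, in SD units, is t(0.975, 14 − k) × √(1/8 + 1/(8 − k)):

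- k = 0: 1.07
- k = 1: 1.12 (+4%)
- k = 2: 1.18 (+10%)
- k = 3: 1.26 (+17%)

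**The case against.** The strongest reply is that an event must be a violation before it can be sorted into a category, and a reduction the plan directs is compliance. On that view the line means allocation or dispensing errors. This may well be the intent, but the text does not say so.

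Second, nothing makes the 5.3 list the Per Protocol exclusion rule. SAP 4.5 asks for a case judgment, and SAP 5.1 requires the reasons for exclusion to be listed, so any removal would be visible. This stands. A reader might infer that reduced subjects will be dropped and the Per Protocol result biased in favour of 100 mg. The documents support neither step: removal is only possible, and its direction is unknown.

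Third, a reader might infer that only the 100 mg arm is exposed. The SAP's written trigger is confined to that arm, but protocol 4.6.1 is arm-neutral and SAP Figure 1 also carries a 25 mg BID label.

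Fourth, a reader might add the under-80% compliance category of SAP 5.3: two of three daily capsules is 67%. This does not support the 100 mg point. Protocol 4.1 supplies a 50 mg dose as a single capsule, so 50 mg TID is still three a day. The BID label has no rule in the SAP text and is not a step-down of the 100 mg arm. The denominator in SAP 7.3, "designated total number of tablets that should have been taken over the study period", can naturally be read as the prescribed regimen.

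Finally, a subject on 50 mg TID receives neither randomized dose, so leaving that subject out of a 25 versus 100 mg Per Protocol comparison can be defended. If that is intended, it should be stated as a rule and not arise from a violation label.

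**Conclusion.** The point holds in a limited form. As worded, SAP 5.3 captures reductions that SAP 3.1 directs and SAP 4.2 allows. On that literal reading the violation table mislabels them whatever happens to the Per Protocol set. Loss from that set is possible, would select on a post-randomization event, and on the SAP's written trigger would fall on the 100 mg arm, with the 25 mg arm not ruled out. Under the assumed 4 of 8 responders and 2 removals, the 100 mg rate could read anywhere from 33% to 67% against 50%.

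The consequence is modest. There is no primary endpoint (SAP 3.3.1), testing is exploratory (SAP 4.6), and the Per Protocol analyses are repeats. The Efficacy and Safety populations both keep reduced subjects, so those analyses, including the safety objective, are unaffected.

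**What to change.** - **SAP 5.3:** limit the category to doses that depart from both the randomized dose and the plan's own reduction rules, that is, allocation, dispensing or dosing errors.
- **SAP 4.5:** state that a reduction or interruption directed by the plan does not by itself exclude a subject from the Per Protocol set.
- **Reporting:** show dose-reduced subjects separately, by randomized arm.
- **Reconciliation:** the exception needs one rule to point to. The documents now differ: protocol 4.1 provides for 75 mg and 50 mg doses, protocol 4.3 mentions only 50 mg, protocol 4.6.1 is arm-neutral, SAP 3.1 directs the step, SAP 4.2 permits it, and SAP Figure 1 adds 25 mg BID. These passages must be reconciled; no view is taken here on which clinical rule is right.

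The cost is a few sentences and one summary, with no new data. Timing needs care. The database was locked on 14 September 2018 and relocked on 19 November 2018, and the SAP amendment was made after lock, whereas Per Protocol membership was due before it. If the clarification changes membership, the Per Protocol tables must be rerun and the change disclosed as post-lock.

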6.2. Medical History

During the Screening Visit, a complete medical history will be collected by subject interviewer. Concomitant medications, recent blood donations, illnesses, and participation in other investigational drug studies will also be recorded. A review of the subject's screening medical history will be performed at the time of presentation on Day 1 (pre-treatment) to update findings including the requirement for an AAPS \geq 4 (from a subject diary) and to document any pretreatment AEs. Medical history will be coded using the Medical Dictionary for Regulatory Activities (MedDRA; Version 21.0).

A summary of medical history, which includes the number (%) of subjects in each treatment group classified according to MedDRA system organ class (SOC) and preferred term (PT) will be provided, as well as a subject listing.

7. TREATMENT AND MEDICATIONS

7.1. Prior and Concomitant Medications

Medications administered prior to but not during study treatment were considered as prior medications. Medications initiated prior to start of study treatment and maintained during the study, or taken during the course of the study, were considered as concomitant medications. Medications with partial or missing start dates were assumed to be concomitant medications, unless there was clear evidence) to suggest that the medications were not taken during study. Prior and concomitant medications will be coded using the World Health Organization (WHO) Drug Dictionary (March 2018).

7.2. Study Treatments

The duration of treatment for each subject will be assessed by descriptively summarizing the number of weeks on drug, both as a continuous and categorical variable (e.g., <1 week). In addition, the average daily dose (mg), total exposure (mg), and total duration of treatment in subject-weeks will be summarized by treatment group and overall.

7.3. Study Treatment Compliance

Compliance will be assessed using subject data recorded in the drug accountability form of the eCRFs. On each day, a subject should take their assigned treatment. The compliance rate for each subject will be computed as $100\% \times (actual number of tablets taken over the study period)/(designated total number of tablets that should have been taken over the study period). Study period is defined as the number of days that the subject has been in the active treatment phase of the trial. Compliance rates will be summarized for each treatment group and overall.$

8. EFFICACY ANALYSES

Complete specifications given below assume that the final sample size will allow for inferential statistical analysis. If the number of subjects analyzed is very low some, or all, inferential procedures will no longer be appropriate.

8.1. Abdominal Pain Score (APS)

For each subject, APS score measured at peak will be averaged over the entire treatment period. Likewise, the APS score measured at trough will be averaged for each subject. The difference (peak - trough) will be calculated, per subject, as mean (peak) - mean (trough).

Mean peak, trough, and peak - trough will be summarized by treatment and overall. The peak - trough differences will be analyzed between treatments using an analysis of covariance (ANCOVA) model with treatment as a factor and Baseline score as a covariate. The 95% CI for the adjusted treatment difference will be presented together with the p-value. For the pooled data, a 1-sample t-test will be conducted testing against the hypothesis of zero difference between peak and trough. The 95% CI for the overall difference between peak and trough assessments will be presented.

Additionally, the APS score measured prior to evening dose (evening trough) will be averaged for each subject. The difference (peak - evening trough) will be calculated, per subject, as mean (peak) - mean (evening trough). The analysis will be repeated using mean peak, evening trough, and peak - evening trough and will be summarized by treatment and overall.

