2.2 Exploratory Objectives

- To determine pharmacokinetic (PK) profiles (including metabolites) and average PK parameters (C_{max}, t_{max}, AUC₀₋₈) of two doses of APD371 TID.
- To assess change in abdominal pain score (APS) from pre-dose (trough) to 1.5 hr post-dose (peak) following the first of 3 daily doses of APD371; assessed daily to Day 56 and averaged weekly to Wk 8
- To assess change in average abdominal pain score (AAPS) from Screening to Wk 8 (averaged weekly to Wk 8)
- To determine the proportion of subjects who are weekly responders
- To determine the proportion of subjects who are end-of-treatment responders
- To determine the number of pain-free days per week in each treatment cohort, based on responses to the APS

- To assess pain medication use in each treatment cohort
- To assess the effect of APD371 treatment on reduction in CRP and other biomarkers at week 4 and week 8
- To assess the effect of APD371 treatment on reduction in fecal calprotectin at week 4 and week 8

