8.7 Efficacy Analysis

8.7.1 Abdominal pain score (APS)

The change in APS scores between morning dose (trough) and 1.5 hr post-treatment first daily dose (peak) assessments will be summarized across all days of treatment and compared by dose cohort and overall. Difference between dose cohort will be reported.

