2.2. Exploratory Objectives

- To determine pharmacokinetic (PK) profiles (including metabolites) and average PK parameters (C_{max}, t_{max}, AUC₀₋₈) of two doses of APD371 three times a day (TID)
- To assess change in abdominal pain score (APS) from pre-dose (trough) to 1.5 hours post-dose (peak) following the first of 3 daily doses of APD371; assessed daily to Day 56 and averaged weekly to Wk 8
- To assess change in average abdominal pain score (AAPS) from Screening to Wk 8 (averaged weekly to Wk 8)
- To determine the proportion of subjects who are weekly responders
- To determine the proportion of subjects who are end-of-treatment (EOT) responders
- To determine the number of pain-free days per week in each treatment cohort, based on responses to the APS

- To assess pain medication use in each treatment cohort
- To assess the effect of APD371 treatment on reduction in C-Reactive Protein (CRP) and other biomarkers at Wk 4 and Wk 8
- To assess the effect of APD371 treatment on reduction in fecal calprotectin at Wk 4 and Wk 8

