3.3.2. Exploratory Endpoints

3.3.2.1. Abdominal Pain Score (APS) and Average Abdominal Pain Score (AAPS)

The APS is a PRO using a numerical rating scale (NRS) which is recorded in a subject diary. The 11-point NRS scale ranges from 0 (no abdominal pain) to 10 (worst possible abdominal pain) will be recorded by subjects in a diary as follows;

During Screening Period

APS is recorded twice daily for at least 7 consecutive days within the Screening period (Day -28 to Day -1), at the following times:

- 1. Early morning, approximately 06:00 08:00
- 2. Late evening, approximately 20:00 22:00

To establish a baseline for AAPS the following procedure will be adopted:

The last diary entry prior to treatment will be identified. The 7 consecutive days that terminate with this last data point constitute the Screening reference period. Baseline for AAPS is the mean of non-missing pain scores within the Screening reference period.

During Treatment Period

APS is recorded three times a day on each treatment Day (Day 1 to 56) at the following times:

- 1. Before the morning dose and before any other morning dose study procedures (i.e., at trough APD371 concentration)
- 2. Approximately 1.5 hours after the morning dose (i.e., at peak APD371 concentration)
- 3. Before the evening dose (i.e., at evening trough ADP371 concentration)

Note: Subjects will also be required to complete the diary before their first morning dose on Wk 0 (Day 1), and at the EOT Visit at Wk 8 in the early morning (06:00 - 08:00). If a subject discontinues the study, ET, the APS score will be assessed.

It should be noted that:

- The AAPS is derived for each assessment period (Wks 1, 2, 4, 6, 8). For Wks 4, 6, and 8 scores are collected from the previous 7 days of diary entries prior to the visit day. 'Peak AAPS' is the mean of non-missing APS recorded at the time of peak concentration for those 7 days. Likewise, 'Trough APS' is the mean of non-missing APS recorded at the time of trough concentration for those 7 days. Similarly, 'Evening Trough APS' is the mean of non-missing APS recorded at the time of evening trough concentration for those 7 days. Wk 1 and Wk 2 peak, trough, evening trough, and overall AAPS are derived in a similar manner but note that:
 - For Wk 1, as Day 1 is neither peak nor trough, and APS scores cannot be accurately identified as pre-dose or post-dose, scores on Day 1 are disregarded. Hence, AAPS scores may be obtained from fewer than 7 days.

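### SAP 8.1 subtracts two whole-period means for the peak-trough effect instead of averaging same-day changes by week, so a pain trend can enter the estimate if peak and trough entries are missing at different times

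*SAP*

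**What the plan says.** **Objective.** SAP 2.2 sets the aim: "To assess change in abdominal pain score (APS) from pre-dose (trough) to 1.5 hours post-dose (peak) following the first of 3 daily doses". The time resolution, in the same words in Protocol 2.2, is "assessed daily to Day 56 and averaged weekly to Wk 8".

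**Derivation.** SAP 8.1 states: "For each subject, APS score measured at peak will be averaged over the entire treatment period". Trough scores are treated the same way, and the difference is "calculated, per subject, as mean (peak) - mean (trough"). That value goes into an ANCOVA comparing the doses and, pooled over doses, into a one-sample t-test against zero. The same construction is repeated with the evening trough.

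**Protocol analysis section.** Under Protocol 8.7.1 the trough-to-peak change "will be summarized across all days of treatment and compared by dose cohort and overall".

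**Missing entries.** Apart from non-responder coding in the responder analyses, SAP 4.7.3 says: "Otherwise, there will be no imputation of missing data". The Efficacy population (SAP 4.5) needs subjects who "have completed at least 7 days of assessments of APS on treatment up to Wk 4", with no requirement for paired readings.

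**Weekly outputs.** SAP 8.2 summarises peak and trough AAPS for Weeks 1, 2, 4, 6 and 8. Its change scores are from Baseline, separately for peak and for trough.

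**Day 1.** For Week 1 AAPS, SAP 3.3.2.1 says "scores on Day 1 are disregarded", because they cannot be reliably labelled as before or after the dose. Section 8.1 does not repeat the rule.

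**The concern.** The objective describes a within-day contrast: the same person, around the same dose, about 1.5 hours apart. Pairing by day removes whatever the pain level was that day. The 8.1 statistic keeps that protection only if the peak and trough entries cover the same days. A day with one of the two readings still feeds one of the two means.

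The 1.5-hour reading is a separate timed entry, so its completion could differ from that of the pre-dose entry. The trial also looks for a change in pain over 8 weeks. If both occur, slow change in pain is counted as acute drug effect, or hides it. With about 16 subjects, a distorted value from one subject carries noticeable weight. Separately, a single whole-period number cannot show whether the acute effect persists, which the weekly wording of the objective asks for.

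**Working it through.** The documents give no effect size, standard deviation, diary completion rate or pain trend for this endpoint, so there is no plan figure to reproduce. The inputs below are assumptions, apart from the formula (SAP 8.1) and the Day 56 end of treatment.

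**1. Algebra.** Let trough pain follow a line with slope b per day, and let the same-day effect be constant. Then

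SAP 8.1 value - true effect = b × (mean day of observed peak entries - mean day of observed trough entries).

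The error is zero if the diaries are complete, if gaps are shared, or if b = 0.

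**2. Main illustration.** Trough pain falls from 6 to 4 over Days 1 to 56, so b = -2/55 = -0.0364. The true effect is -0.50. Trough entries are complete on Days 2 to 56, with mean day 29.

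| Peak entries | Mean peak day | Error | SAP 8.1 value | Same-day mean |
|---|---|---|---|---|
| Missing rate rises 0 to 50% | 25.89 | -0.0364 × -3.11 = +0.11 | -0.39 | -0.50 |
| Missing rate falls 50% to 0 | 32.11 | -0.0364 × 3.11 = -0.11 | -0.61 | -0.50 |
| Stop after Day 28 | 15 | -0.0364 × -14 = +0.51 | +0.01 | -0.50 |

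**3. Varying the trend.** Over Days 1 to 56 with complete trough entries, for a total fall of 0, 1, 2 or 3 points:

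- peak entries missing in the last 14 days: -0.50, -0.37, -0.25, -0.12;
- missing in the first 14 days: -0.50, -0.63, -0.75, -0.88;
- missing every second day: at most 0.03 from -0.50.

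**4. Random gaps.** Peak entries are missing at random at 30% and trough entries at 10%. The assumed day-to-day SD is 1.5 and the within-day SD 0.7 (20,000 repeats). There is no bias, but the per-subject SD of the estimate is about 0.19, against 0.12 for same-day pairs.

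**5. Loss of the weekly course.** If the true effect fades linearly from -1 to 0, the whole-period mean is -0.50 even with complete data, while Week 1 is -0.95 and Week 8 is -0.05.

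**6. Does pairing alone repair it?** Take the fading effect (-1 on Day 2 to 0 on Day 56) with the rising gap pattern of step 2.

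- Same-day pairs averaged over days: -1 + (25.89 - 2)/54 = -0.56.
- SAP 8.1 formula: -0.56 + 0.11, about -0.44.
- Same-day pairs averaged within weeks, weeks weighted equally: within about 0.01 of -0.50.

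The first two miss by similar amounts, so the weighting must be specified. If peak entries stop after Day 28, the pairs cover only Days 2 to 28 (mean day 15) and give -1 + 13/54 = -0.76. No weighting recovers weeks without pairs.

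**The case against.** A reader might infer that uneven missing entries bias the estimate in themselves. The documents do not support that. Peak and trough gaps must fall at different times and pain must also trend, or gaps must depend on that day's pain. Both readings come from one diary, and early termination removes both from then on. Nothing in the documents makes a long run of missing peak entries beside complete trough entries likely.

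A reader might also infer that the SAP departs from the protocol's planned analysis. It does not on pooling: Protocol 8.7.1 itself summarises over all treatment days. The mismatch is with the objective. What 8.7.1 pools, however, is the change, so an average of daily changes would satisfy both sections.

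The weekly course is not wholly invisible either. SAP 8.2 gives weekly peak and trough means, Figure 14.2.1 plots them, and Table 14.2.4 summarises daily scores. These are separate levels of non-missing scores, without a specified paired difference.

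On Day 1, a reader might infer that unlabelled scores certainly enter 8.1. SAP 3.3.2.1 already treats Day 1 as belonging to neither category, so it can be read as excluded. The rule is written under Week 1 AAPS, and at most one day in 56 is affected.

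Finally, if trend and gap pattern are alike in the two dose groups, the error cancels in the between-dose ANCOVA. Protocol 8.1 calls the p-values nominal, and SAP 8 allows inference to be dropped if numbers are very low. These points stand and limit the weight of the concern.

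**Conclusion.** The point holds in a limited form. SAP 8.1 does not compute the quantity in the objective: it has no same-day pairing and no weekly peak-trough change, and no other section supplies them. The two quantities agree when diaries are complete or gaps are shared. Otherwise a pain trend can leak in, chiefly in the pooled one-sample test.

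The actual size is unknown. The shift of about 0.11 for gradual gaps rests on an assumed 2-point fall, a constant effect of -0.50 and complete trough entries. The near-zero result is an extreme case, not a forecast. For an exploratory endpoint this is a worthwhile improvement, not a threat to the trial's conclusions.

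**What to change.** In SAP 8.1:

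1. Compute peak minus trough for each day from Day 2 to Day 56 that has both readings.
2. Average within each week. Take the equally weighted mean of the weekly values as the subject's overall value.
3. Use that value in the planned ANCOVA and one-sample t-test.
4. Report the weekly means and the number of paired days per subject, so that weeks without pairs are visible.
5. State that Day 1 is excluded, in line with SAP 3.3.2.1.

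The cost is programming only: no new data are needed, and AAPS is already derived from the raw diary entries. Because SAP Amendment 1 postdates database lock, record the change as post-lock and show the existing 8.1 result beside it.
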